#### Development of a Milled Formulation of TAK-228

In order to allow more predictable absorption of TAK-228 after oral administration and to allow scale-up manufacturing of TAK-228 capsules, Millenium/Takeda developed a new milled formulation of the agent. The physical milling step during the granulation process controls particle size distribution of TAK-228. In

order to observe whether this milling step altered the safety and PK profile of TAK-228, the company performed in vivo studies with PK analysis of milled TAK-228. These studies indicated that the milled formulation may result in faster absorption with possibly higher maximum concentration ( $C_{max}$ ), which could result in a different safety profile, compared to the previous unmilled API capsules.

Takeda developed new TAK-228 capsules containing milled active pharmaceutical ingredient (API) for clinical studies in 1 mg, 3 mg, and 5 mg strengths. Patients receiving the milled formulation were added onto ongoing studies C31001 and C31002, as well as a new study MLN0128-1004, with various treatment cohorts including daily and weekly administration of milled TAK-228.

The recommended dose of milled TAK-228 was evaluated in 17 patients of MLN0128-1004, with PK, safety, and tolerability assessed. Six patients were given a 4 mg QD dose of milled TAK-228 and 3 patients had observed DLT (rash, appetite loss and fatigue). A dose of 3 mg QD was given to 11 patients with only 1 DLT (decreased platelets) observed. The 3 mg QD dose of TAK-228 was declared the RP2D, and was generally well tolerated and demonstrating objective responses in patients.

The significant difference in tolerability observed in the comparison of the MTDs between unmilled and milled TAK-228 when administered QD may be possibly explained due to the effect of food on the safety/tolerability of unmilled TAK-228 in study IND128-001. The GastroPlusTM simulation performed under fasting conditions on the trial demonstrated that unmilled and milled TAK-228 administration result in comparable exposures to TAK-228; whereas in the fed state, milled TAK-228 resulted in higher  $C_{max}$  (1.5- to 2-fold higher) and earlier  $T_{max}$  than unmilled TAK-228 with comparable AUCs. Consequently, a dose of 3 mg QD was chosen as the RP2D of milled TAK-228 dose in empty stomach conditions.

The RP2D for milled TAK-228 on a weekly schedule was determined to be 30 mg, the same weekly RP2D as seen for the older unmilled formulation. Six patients treated at 30 mg weekly with the milled formulation did not demonstrate any DLT, but the agent was not escalated further. No DLT had been demonstrated for milled TAK-228 at the prior 20 mg QW dose as well.

TAK-228-1004, a phase I, open label study to evaluate the safety, tolerability, and pharmacokinetics of TAK-228 in combination with paclitaxel in adult patients with advanced non-hematological malignancies), with the new milled API was used to determine the recommended phase 2 dose (RP2D) for TAK-228 QD×3 days per week in combination with paclitaxel. The RP2D of milled TAK-228, given 3 consecutive days weekly, in combination with weekly paclitaxel at 80 mg/m^2, was 6 mg.

[figure not shown]
## 2.4 Rationale

While the existing data suggest that TORC1 inhibition may modestly inhibit Nrf2 signaling and cell viability in *NFE2L2* mutant models, the activation of concurrent Akt signaling in *NFE2L2* mutant cell lines, increased efficacy of BEZ235 in the above pre-clinical models, as well the prior experimental data demonstrating a bypass pathway through TORC2/Akt supports the use of dual TORC1/TORC2 inhibition.

[figure not shown]
To strengthen the rationale for the use of MLN0128 (TAK-228) in squamous lung cancers harboring *NFE2L2* and *KEAP1* mutations, we performed cytotoxicity and signaling experiments in both *NFE2L2* mutant (LK-2) and *KEAP1* mutant (H460, A549, H838) lung cancer cell lines treated with MLN0128

(TAK-228) and a number of rapalogs. We note that while LK-2 cells are squamous cell in histology, all *KEAP1* mutant cell lines were either adenocarcinomas or large cell carcinomas (no *KEAP1* mutant squamous cell lung cancer cell line exists to our knowledge). An Alamar blue assay was used to assess the effect of MLN0128 (TAK-228), rapamycin, everolimus, and deforolimus on cell viability in a dose response manner as shown below in

**Figure 5.**

[figure not shown]
[figure not shown]

No cytotoxic effect was observed for any of the rapalogs tested against any cell line at any drug concentration. Conversely, MLN0128 (TAK-228) was associated with a low nanomolar IC50 for cytotoxicity in *NFE2L2* mutant LK2 cells and a relatively low IC50 for the *KEAP1* null (*KEAP1* G333C mutant + *KEAP1* loss) A549 cells. Squamous cell lung cancer SK-MES-1 cells WT for *NFE2L2* and *KEAP1* showed no response to MLN0128 (TAK-228). With regard to the differential response in A549 cells compared to the two other *KEAP1* mutant cell lines tested, loss of heterozygosity may potentiate response to drug. It is worth reiterating that A549 cells were found to be sensitive to MLN0128 (TAK-228) by Millenium in their pre-clinical data as well. Alternatively, not all mutations in *KEAP1* may predict for sensitivity to drug inhibition.

**Figure 6.** Bar graph plot of total phospho-S6 (Ser240/244) staining intensity. Cell lines are represented by color scale: H460 in gray, A549 in blue, H838 in green, SK-MES-1 in red, and LK-2 in pink. Increasing drug concentration is symbolized by the triangles (0, 0.001, 0.1 and 10  $\mu$ M dose levels)

[figure not shown]
To determine the downstream effect of each drug on mTOR signaling, cells were fixed and incubated with a phospho-S6 (Ser240/244) antibody after 2 hours of drug exposure. As seen in [Figure 6](#), a dose-dependent decrease in S6 phosphorylation was generally seen across the cell lines in response to each drug. Importantly, inhibition of S6 phosphorylation in LK-2 and A549 cells was substantially greater in response to MLN0128 (TAK-228) compared to the rapalogs at 100nM concentrations ([Figure 7 and 8](#)).

[figure not shown]
**Figures 7 and 8.** Bar graph plot of relative phospho-S6 (Ser240/244) staining intensity at 100nM drug concentrations in *NFE2L2* mutant LK-2 cells (left) and *KEAP1* mutant A549 cells (right). Data are shown relative to DMSO control.

Taken together, these data suggest that MLN0128 (TAK-228) will be superior to the TORC1 rapalogs at inhibiting downstream mTOR signaling and at inducing cell death in *NFE2L2* mutant and a subset of *KEAP1* mutant lung cancers, providing strong rationale for its use in patients with these oncogenic genotypes.

Cell line xenograft studies indeed bear this out in both our *NFE2L2* mutant squamous cell lung cancer (LK-2) and *KRAS* mutant/*KEAP1* inactivated (A549) contexts (**Figure 9** and **Figure 10**) where MLN0128 (TAK-228) treatment leads to a decrease in the size of generated tumors.

**Figure 9.** Differential anti-tumor effect of the TORC1/2 inhibitor MLN0128/TAK-228 against the rapalogs everolimus and deforolimus in an LK-2 *NFE2L2* mutant squamous cell lung cancer xenograft. Decrease in tumor volume was seen only in xenografts treated with MLN0128/TAK-228 (-55% tumor reduction).

**Figure 10.** Anti-tumor effect of the TORC1/2 inhibitor MLN0128/TAK-228 against an A549 *KRAS* mutant/*KEAP1* null lung cancer xenograft. MLN0128/TAK-228 led to a decrease in tumor volume not seen with the glutaminase inhibitor CB-839.

## 2.5 Correlative Studies Background

### mTOR inhibition

Inhibition of TORC1/2 signaling by MLN0128 (TAK-228) leads to changes in phosphorylation of the TORC1 downstream targets S6 and 4EBP1 ( $\downarrow$ pS6 and p4EBP1) and a TORC2 target AKT ( $\downarrow$ pAKT) in cell lines of various tumor types and genetic backgrounds, such as HER2-amplified trastuzumab-sensitive and –resistant breast cancer cells (De et al., 2012), breast ductal T47D cell line with PI3KCA mutation (Investigator's Brochure), metastatic RCC (Wang et al., 2011), endometrial cell lines (Kessler et al., 2012), and prostate cancer line PC-3 with PTEN deletion (Investigator's Brochure). Dual TORC1/2 inhibition mitigates the feedback activation of AKT, known to cause resistance to TORC1-selective inhibitors such as rapamycin (De et al., 2012). Its effect in squamous cell lung cancer models with *NFE2L2* and *KEAP1* mutations is shown in Section 2.3, where a decrease in pS6 and p4EBP1 was also seen.

### Reverse phase protein array analysis (RPPA)

There are a number of practical limits associated with pharmacodynamic testing in cancers where the majority of tissue material comes from small needle core biopsies. These include tumor heterogeneity necessitating microdissection, small total protein yields, the need to snap-freeze samples at -80C to preserve phosphoprotein stability, and the demand for a quantitative assay. Immunohistochemistry, which is the most readily available proteomic test, is hampered by its qualitative nature. Western blotting, which can be quantitative depending on the specificity of the antibody used, has poor multiplex capabilities.

This study incorporates reverse phase protein array (RPPA) analysis as an exploratory biomarker analysis to determine the pharmacodynamic effect of MLN0128 (TAK-228) in optional pre- and on-treatment tumor biopsies. RPPA is a highly multiplex quantitative proteomic platform that can test for both phosphorylated and non-phosphorylated proteins. [name] at MD Anderson will perform RPPA on these optional paired tumor specimens. A panel of 156 validated antibodies (217 total) is available for testing simultaneously, including key targets for this proposal (p4EBP1, pS6K, AKT pS463 and pT308). We will determine, in descriptive terms, changes in phosphorylation in these specific downstream targets in response to MLN0128 (TAK-228).

Tumor samples will be snap-frozen in liquid nitrogen and stored at -80C. This material will then be shipped frozen to [name] laboratory at MD Anderson for analysis.

## 3. PATIENT SELECTION

### 3.1 Eligibility Criteria

3.1.1 Patients must have histologically or cytologically confirmed stage IV or recurrent squamous cell lung cancer or *KRAS* mutant lung cancer that harbors any of the *NFE2L2* mutations or *KEAP1* mutations below. Prioritized *KEAP1* mutations are shown below, but any *KEAP1* mutation will be eligible.

Eligible and functionally validated Nrf2 amino acids/ mutations (Appendix B)			
NFE2L2 mutation sites	Domain	Function	Validation
aa.17-36	DLG motif	Keap1 binding site	in silico and in vitro
aa.76-82	ETGE motif	Keap1 binding site	in silico and in vitro
K44, K50, K52, K53, K56, K64, K68	Lysine ubiquitination targets	Nrf2 degradation	in silico and in vitro
Exon 2 deletion	DLG/ETGE motifs	Keap1 binding site	in vitro

Eligible and functionally validated Keap1 amino acids/mutations (Appendix B)			
KEAP1 mutation sites	Domain	Function	Validation
R380, R415, R483	DGR-CTR	Nrf2 binding residues	in silico and in vitro
Y525, Q530, N382, Y573, F577, Y334, S363, S602, S555	DGR-CTR	Nrf2 binding cavity	in silico and in vitro
G364C, G430C	DGR-CTR	Nrf2 binding cavity	in silico and in vitro
aa.315-624	DGR-CTR	Nrf2 binding domain	in silico
aa.96-100	BTB HKVVL	Keap1 dimerization	in silico and in vitro
C151, V155, V167	BTB	electrophile sensor	in vitro
D244, S243, C273, C288	IVR	electrophile sensor	in vitro
Any frameshift or nonsense mutation	N/A	N/A	N/A

- 3.1.2 Patients must have measurable disease, defined as at least one lesion that can be accurately measured in at least one dimension (longest diameter to be recorded for non-nodal lesions and short axis for nodal lesions) as  $\geq 20$  mm ( $\geq 2$  cm) with conventional techniques or as  $\geq 10$  mm ( $\geq 1$  cm) with spiral CT scan, MRI, or calipers by clinical exam. See Section 11 for the evaluation of measurable disease.
- 3.1.3 Patients must have completed at least 1 prior line of systemic therapy. Patients who have declined first line therapy or for whom first-line therapy would be clinically inappropriate, will be considered eligible for the trial.
- 3.1.4 Age  $\geq 18$  years. Because no dosing or adverse event data are currently available on the use of MLN0128 (TAK-228) in patients  $< 18$  years of age and because lung cancer is rare in this age group, children are excluded from this study.
- 3.1.5 ECOG performance status  $\leq 2$  (Karnofsky  $\geq 60\%$ , see Appendix A).
- 3.1.6 Life expectancy of greater than 3 months.
- 3.1.7 Patients must have normal organ and marrow function as defined below:
- leukocytes  $\geq 3,000/\text{mcL}$
  - absolute neutrophil count  $\geq 1,500/\text{mcL}$
  - platelets  $\geq 100,000/\text{mcL}$

composition to MLN0128 (TAK-228).

- 3.2.5 Uncontrolled intercurrent illness including, but not limited to, ongoing or active infection, symptomatic congestive heart failure, hypertension, unstable angina pectoris, cardiac arrhythmia, or psychiatric illness/social situations that would limit compliance with study requirements. No ischemic myocardial or cerebrovascular event, class III or IV heart failure, placement of pacemaker, or pulmonary embolism within six months of receiving first dose of MLN0128 (TAK-228).
- 3.2.6 Baseline prolongation of the rate-corrected QT interval (QTc) > 480 milliseconds, or history of congenital long QT syndrome, or torsades de pointes.

Pregnant women are excluded from this study because MLN0128 (TAK-228) is an mTOR agent with the potential for teratogenic or abortifacient effects. Because there is an unknown but potential risk for adverse events in nursing infants secondary to treatment of the mother with MLN0128 (TAK-228), breastfeeding should be discontinued if the mother is treated with MLN0128 (TAK-228).

- 3.2.7 Patients previously treated with an mTOR or PI3K inhibitor.
- 3.2.8 Concomitant administration of any proton pump inhibitor (PPI) is not permitted during the study. Patients receiving PPI therapy before enrollment must stop using the PPI for 7 days before their first dose of study drugs.
- 3.2.9 Uncontrolled diabetes mellitus (Fasting plasma glucose > 130mg/dL despite optimal medical management of hyperglycemia)
- 3.2.10 Known hepatitis B surface antigen-positive, or known or suspected active hepatitis C infection
- 3.2.11 Patients receiving histamine H2 receptor antagonists before enrollment must stop using these medications for at least 24 hours before their first dose of study drug. See section 5.2 for further details on the use of histamine H2 receptor antagonists.

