#### 11.1.1 Definitions

Evaluable for toxicity. All patients will be evaluable for toxicity from the time of their first treatment with MLN0128 (TAK-228).

Evaluable for objective response. Only those patients who have measurable disease present at baseline, have received at least one cycle of therapy, and have had their disease re-evaluated will be considered evaluable for response. These patients will have their response classified according to the definitions stated below. (Note: Patients who exhibit objective disease progression prior to the end of cycle 1 will also be considered evaluable.)

Evaluable Non-Target Disease Response. Patients who have lesions present at baseline that are evaluable but do not meet the definitions of measurable disease, have received at least one cycle of therapy, and have had their disease re-evaluated will be considered evaluable for non-target disease. The response assessment is based on the presence, absence, or unequivocal progression of the lesions.

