#### 11.1.2 Disease Parameters

Measurable disease. Measurable lesions are defined as those that can be accurately measured in at least one dimension (longest diameter to be recorded) as  $\geq 20$  mm ( $\geq 2$  cm) by chest x-ray or as  $\geq 10$  mm ( $\geq 1$  cm) with CT scan, MRI, or calipers by clinical exam. All tumor measurements must be recorded in millimeters (or decimal fractions of centimeters).

Note: Tumor lesions that are situated in a previously irradiated area might or might not be considered measurable.

Malignant lymph nodes. To be considered pathologically enlarged and measurable, a lymph node must be  $\geq 15$  mm ( $\geq 1.5$  cm) in short axis when assessed by CT scan (CT scan

slice thickness recommended to be no greater than 5 mm [0.5 cm]). At baseline and in follow-up, only the short axis will be measured and followed.

Non-measurable disease. All other lesions (or sites of disease), including small lesions (longest diameter <10 mm [<1 cm] or pathological lymph nodes with  $\geq 10$  to <15 mm [ $\geq 1$  to <1.5 cm] short axis), are considered non-measurable disease. Bone lesions, leptomeningeal disease, ascites, pleural/pericardial effusions, lymphangitis cutis/pulmonitis, inflammatory breast disease, and abdominal masses (not followed by CT or MRI), are considered as non-measurable.

Note: Cystic lesions that meet the criteria for radiographically defined simple cysts should not be considered as malignant lesions (neither measurable nor non-measurable) since they are, by definition, simple cysts.

‘Cystic lesions’ thought to represent cystic metastases can be considered as measurable lesions, if they meet the definition of measurability described above. However, if non-cystic lesions are present in the same patient, these are preferred for selection as target lesions.

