Target lesions. All measurable lesions up to a maximum of 2 lesions per organ and 5 lesions in total, representative of all involved organs, should be identified as **target lesions** and recorded and measured at baseline. Target lesions should be selected on the basis of their size (lesions with the longest diameter), be representative of all involved organs, but in addition should be those that lend themselves to reproducible repeated measurements. It may be the case that, on occasion, the largest lesion does not lend itself to reproducible measurement in which circumstance the next largest lesion which can be measured reproducibly should be selected. A sum of the diameters (longest for non-nodal lesions, short axis for nodal lesions) for all target lesions will be calculated and reported as the baseline sum diameters. If lymph nodes are to be included in the sum, then only the short axis is added into the sum. The baseline sum diameters will be used as reference to further characterize any objective tumor regression in the measurable dimension of the disease.

Non-target lesions. All other lesions (or sites of disease) including any measurable lesions over and above the 5 target lesions should be identified as **non-target lesions** and should also be recorded at baseline. Measurements of these lesions are not required, but the presence, absence, or in rare cases unequivocal progression of each should be noted throughout follow-up.

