#### **13.3.2 Evaluation of Response**

All patients included in the study must be assessed for response to treatment, even if there are major protocol treatment deviations or if they are ineligible. Each patient will be assigned one of the following categories: 1) complete response, 2) partial response, 3) stable disease, 4) progressive disease, 5) early death from malignant disease, 6) early death from toxicity, 7) early death because of other cause, or 9) unknown (not assessable, insufficient data). [Note: By arbitrary convention, category 9 usually designates the “unknown” status of any type of data in a clinical database.]

All of the patients who met the eligibility criteria (with the possible exception of those who received no study medication) should be included in the main analysis of the response rate. Patients in response categories 4-9 should be considered to have a treatment failure (disease progression). Thus, an incorrect treatment schedule or drug administration does not result in exclusion from the analysis of the response rate. Precise definitions for categories 4-9 will be protocol specific.

All conclusions should be based on all eligible patients. Subanalyses may then be performed on the basis of a subset of patients, excluding those for whom major protocol deviations have been identified (*e.g.*, early death due to other reasons, early discontinuation of treatment, major protocol violations, etc.). However, these subanalyses may not serve as the basis for drawing conclusions concerning treatment efficacy, and the reasons for excluding patients from the analysis should be clearly reported. The 95% confidence intervals should also be provided.

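### Section 3.1.2 accepts a lymph node of 10 to under 15 mm short axis on CT as measurable disease and 11.1.2 does not, so a patient can enrol with no target lesion and no route to a partial response

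*Combined protocol and SAP*

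**What the plan says.** Section 3.1.2 requires at least one measurable lesion. It names the dimension for each type ("longest diameter to be recorded for non-nodal lesions and short axis for nodal lesions") and sets at least 20 mm by conventional techniques, or at least 10 mm by spiral CT, MRI or calipers. It gives no separate threshold for nodes. It closes with "See Section 11 for the evaluation of measurable disease".

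Section 11.1.2 repeats the general 20 mm and 10 mm limits and then adds a nodal rule: "To be considered pathologically enlarged and measurable, a lymph node must be" at least 15 mm in short axis on CT. Its list of non-measurable disease includes pathological nodes of 10 to under 15 mm short axis. Target lesions come from this definition: "All measurable lesions up to a maximum of 2 lesions per organ and 5 lesions in total".

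Two sections say who counts for response. Section 11.1.1 limits evaluability to "Only those patients who have measurable disease present at baseline, have received at least one cycle of therapy, and have had their disease re-evaluated", with an exception for objective progression before the end of cycle 1. Section 13.3.2 puts "All of the patients who met the eligibility criteria" into the main response-rate analysis, apart possibly from those who received no drug.

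**The concern.** The two sections give opposite answers for the same node. Site staff confirm eligibility against the Patient Selection section and a checklist (Section 4.3), so the 10 mm figure is the one that admits the patient. Response is then scored under Section 11, where that node is not a target lesion.

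The primary endpoint is CR plus PR in each cohort. A patient without target lesions has one of these two routes closed by definition, and the two sections on evaluability disagree on whether that patient is in the denominator. The cohorts are small (9, 5 and 5 patients reported in Section 13.1), so one patient visibly changes a response rate. Section 13.1 adds patients partly to make that rate more precise, and 3.1.2 still governs who they are.

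**Working it through.** **1. The definitions side by side, for a node measured on CT**

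| Short axis | 3.1.2 | 11.1.2 |
|---|---|---|
| under 10 mm | not measurable | not measurable |
| 10 to under 15 mm | measurable | non-measurable |
| 15 mm or more | measurable | measurable |

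The conflict is confined to the middle row. It matters only when such a node is the patient's sole qualifying lesion.

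**2. Following that patient through the response rules**

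- Target lesions are chosen from measurable lesions (11.1.2), so there are none.
- PR is a fall of at least 30% in the target-lesion sum (11.1.4.1), so it cannot be computed.
- The response table for non-measurable disease (11.1.4.3) offers CR, non-CR/non-PD, not evaluated and PD. It has no PR row.
- CR stays open: 11.1.4.2 requires non-target disease to disappear, tumor markers to normalize and nodes to be under 10 mm.
- Non-CR/non-PD is not among the outcome categories listed in 13.3.2.

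**3. How hard the CR route is**

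If the node is the only disease, the shrinkage needed from baseline short axis d to the 10 mm limit is (d − 10)/d:

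- d = 12 mm: 2/12 = 16.7%
- d = 14 mm: 4/14 = 28.6%
- d = 10/0.7 = 14.3 mm: 30%, the same as PR
- d approaching 15 mm: 5/15 = 33.3%

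For most of the range, this is less than PR would demand. If other non-measurable disease is present, all of it must also resolve, and CR becomes harder. The direction of the effect therefore depends on the patient.

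**4. The plan's own design figure**

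Inputs from 13.1: 5 patients then 10, stop at 0 responses in 5, success at 2 or more in 10, rates 5% and 40%. The probability of success is 1 − (1−p)^5 − 5p(1−p)^4 × (1−p)^5.

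- p = 0.40: 1 − 0.0778 − 0.2592 × 0.0778 = 0.902, which reproduces the stated 90%.
- p = 0.05: 1 − 0.7738 − 0.2036 × 0.7738 = 0.069, within the stated 10%.

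Reconciling the node definition changes neither figure.

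**5. What one affected patient does to a reported rate**

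Assume one affected non-responder, who is then excluded. Intervals are exact 95%.

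- Cohort 1: 2/9 = 22% (3% to 60%) becomes 2/8 = 25% (3% to 65%).
- Cohort 2 or 3: 0/5 becomes 0/4. The upper limit, 1 − 0.025^(1/n), moves from 52% (n = 5) to 60% (n = 4).

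These are illustrations. The documents do not report that any such patient was enrolled.

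**The case against.** The strongest defence is that 3.1.2 sends the reader to Section 11, where the 15 mm rule follows directly after the same general limits, and that a single institution is likely to apply it. This makes misapplication less likely. It does not remove the conflict: 3.1.2 states a complete numeric definition of its own, names nodes in it, and refers to Section 11 only for evaluation.

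A second defence is that patients with stage IV or recurrent lung cancer will rarely have a 10 to under 15 mm node as their sole qualifying lesion. That is plausible, and nothing in the documents contradicts it.

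A reader might infer that such a patient cannot respond at all and that the design loses power. With zero chance of response for one patient in stage 1, the formula gives 1 − 0.6^4 − 4(0.4)(0.6^3)(0.6^5) = 84.4% instead of 90.2%, and the chance of a wrong stage 1 stop rises from 7.8% to 13.0%. The documents do not support this as an effect, because CR remains available and can need less shrinkage than PR. The two-stage decisions have also largely been made: cohort 1 has its 2 responses, cohort 2 is being extended despite 0/5, cohort 3 is closing, and no pass/fail rule is stated for the extension.

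A reader might also infer that correcting 3.1.2 would settle the response denominator. It would not. Sections 11.1.1 and 13.3.2 also differ for an eligible patient who lacks a full cycle or a re-evaluation, whatever the node size.

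**Conclusion.** The contradiction is real, is in current text, and bears on the primary endpoint. A patient whose only qualifying lesion is a node of 10 to under 15 mm on CT meets 3.1.2, has no target lesion, cannot be PR, and is placed differently by 11.1.1 and 13.3.2. The size is unknown because no frequency is given, and the bias could run either way through the CR route. The practical stake is who enters the extension of cohorts 1 and 2 and how the rates already observed are read. The sample size and the original decision rules are unaffected. A reader might suspect that the 0/5 results arose this way. Nothing in the documents shows that they did, and only a look at the baseline lesions can answer it.

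The conclusion is limited to CT. Section 11.1.3 accepts superficial lesions, including palpable nodes, of at least 10 mm by calipers, and 3.1.2 agrees with it there.

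**What to change.** Align 3.1.2 with Section 11 before the extension patients enter cohorts 1 and 2. Measurable disease would be any one of:

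- a non-nodal lesion of at least 10 mm longest diameter by CT or MRI, or at least 20 mm by chest x-ray;
- a lymph node of at least 15 mm short axis by CT;
- a superficial lesion, including a palpable node, of at least 10 mm by calipers, as in 11.1.3.

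The caliper clause is needed. Without it, the new wording would exclude patients whom 11.1.3 treats as measurable.

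Check the baseline target lesions of all patients already enrolled (9 + 5 + 5 = 19 reported in 13.1). Report any who qualified only through a 10 to under 15 mm node on CT, and give a sensitivity response rate with its exact 95% interval that excludes them.

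The cost is one amended sentence in the protocol, the matching line of the eligibility checklist, and a short review of baseline lesion records. The downside is that a rare node-only patient would no longer qualify. The wider difference between 11.1.1 and 13.3.2 on the denominator needs its own correction.
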